### **5.2 Outliers**

No specific criteria for outliers will be applied. Rather, relevant parameters (Serum creatinine, Hematocrit, weight, NT-Pro-BNP, eGFR, and all measurements done by FAST) will be inspected by tables and figures (including histograms, kernel density plots, normal Q-Q-plots, boxplots) during the data review (see section 6). Further, for each patient the time series of weight, serum creatinine, and hematocrit will be displayed graphically to identify outliers or data errors.

## **6 Data review meeting**

After the data base lock (i.e. after all queries are solved within the data management process) and before the analysis, a data review meeting will be held in order to assign patients to the analysis populations, to determine the amount of missing values for the concentrations of FD003, and to identify any remaining data errors and decide on their handling. The results of this meeting and possible changes or additions to the analysis including reasons will be documented in a data review report. Prior to the data review a set of tables, listings and figures will be defined to be used.

## **7 Statistical analyses / methods**

### **7.1 General remarks**

The primary objective is to assess the safety and function of the FAST PV and mGFR Technology in hospitalized patients with heart failure. This is a phase II trial. No formal hypothesis test is performed to assess the primary objective. This is justified as follows: 1. Both function and safety cannot be uniquely assessed by one specific endpoint, but there exist several relevant endpoints and endpoint-related criteria which must be investigated in order to assess the global function and safety. 2. For reasons of feasibility, the studies sample size is limited to 50 patients which is an adequate number in the context of a phase II trial. However, this limited number does not allow to address a complex multiple testing problem with adequate power.

Therefore, all analyses including p values are purely descriptive. The aim is to generate new hypotheses to be tested in subsequent phase III trials.

For continuous variables descriptive statistics include mean, standard deviation, median, inter quartile range and range. For categorical variables descriptive statistics include absolute and relative frequencies.

Due to the low number of patients in one of the centers, no adjustment for center will be done in the analyses.

## 7.2 Derived Parameters

The following formulas will be used for determination of estimated and measured TBV, ideal TBV, estimated and measured total blood volume status (eTBVS and mTBVS), ePV, estimated PV change, ideal PV, estimated and measured plasma volume status (ePVS and mPVS), and eGFR on day 1 and day 3:

Nadler formula for eTBV (Sharma & Sharma, 2020):

- Men:  $eTBV [L] = (0.3669 \times \text{Height [m]}^3) + (0.03219 \times \text{Weight [kg]}) + 0.6041$
- Women:  $eTBV [L] = (0.3561 \times \text{Height [m]}^3) + (0.03308 \times \text{Weight [kg]}) + 0.1833$

mTBV will be calculated as follows:

- $mTBV [mL] = mPV [mL] / (1 - \text{hematocrit [\%]} / 100)$

Lemmens-Bernstein-Brodsky formula for ideal TBV (iTBV) (Lemmens, Bernstein, & Brodsky, 2006):

- $iTBV [mL/kg] = 70 / [\text{sqrt}(\text{body mass index}/22)]$  – the lowest body weight during the days 1 to 5 will be used for calculation of BMI
- $iTBV [mL] = iTBV [ml/kg] \times \text{weight [kg]}$  – the lowest body weight during the days 1 to 5 will be used for calculation

Estimated and measured total blood volume status:

- $eTBVS [\%] = \text{Percentage change from iTBV: } (eTBV - iTBV) / iTBV$
- $mTBVS [\%] = \text{Percentage change from iTBV: } (mTBV - iTBV) / iTBV$

Kaplan-Hakim Formula for ePV (Ling et al., 2015):

- Men:  $ePV [mL] = (1 - \text{hematocrit [\%]}) \times [1530 + (41 \times \text{weight [kg]})]$
- Women:  $ePV [mL] = (1 - \text{hematocrit [\%]}) \times [864 + (47.9 \times \text{weight [kg]})]$

Strauss formula for plasma volume change (Strauss, Davis, Rosenbaum, & Rossmeis, 1951):

- $PV\_2/PV\_1 \times 100 [\%] = \text{hemoglobin\_1 [g/dL]} / \text{hemoglobin\_2 [g/dL]} \times (1 - \text{hematocrit\_2 [\%]}) / (1 - \text{hematocrit\_1 [\%]}) \times 100$

Plasma volume change will also be calculated via the ratios of ePV by the Kaplan-Hakim-Formula

Harrison formula for ideal PV (iPV) (from Ling 2015):

- Men: iPV [mL] = 39 [mL/kg] × weight [kg] – the lowest body weight during the days 1 to 5 will be used for calculation
- Women: iPV [mL] = 40 [mL/kg] × weight [kg] – the lowest body weight during the days 1 to 5 will be used for calculation

Estimated and measured plasma volume status (ePVS and mPVS):

- ePVS [%] = Percentage change from iPV: (ePV - iPV)/iPV
- mPVS [%] = Percentage change from iPV: (mPV - iPV)/iPV

The eGFR will be calculated using CKD-EPI formula (Levey et al., 2009):

- $$\text{eGFR [mL/min/1.73 m}^2\text{]} = 141 \times \min(\text{serum creatinine [mg/dL]/}\kappa, 1)^\alpha \times \max(\text{serum creatinine [mg/dL]/}\kappa, 1)^{-1.209} \times 0.993^{\text{age [years]}} \times 1.018 \text{ [if female]} \times 1.159 \text{ [if Black]}$$
- $\kappa = 0.7$  (females) or  $0.9$  (males)
- $\alpha = -0.329$  (females) or  $-0.411$  (males)

The eGFR will also be calculated by the CKD-EPI cystatin C formula (Inker et al., 2012):

- $$\text{eGFR [mL/min/1.73 m}^2\text{]} = 133 \times \min(\text{cystatin C [mg/L]/}0.8, 1)^{-0.499} \times \max(\text{cystatin C [mg/L]/}0.8, 1)^{-1.328} \times 0.996^{\text{Age [years]}} \times 0.932 \text{ [if female]}$$

The eGFR will additionally be calculated by the CKD-EPI creatinine-cystatin C formula (Inker et al., 2012):

- $$\text{eGFR [mL/min/1.73 m}^2\text{]} = 135 \times \min(\text{serum creatinine [mg/dL]/}\kappa, 1)^\alpha \times \max(\text{serum creatinine [mg/dL]/}\kappa, 1)^{-0.601} \times \min(\text{cystatin C [mg/L]/}0.8, 1)^{-0.375} \times \max(\text{cystatin C [mg/L]/}0.8, 1)^{-0.711} \times 0.995^{\text{Age [years]}} \times 0.969 \text{ [if female]} \times 1.08 \text{ [if black]}$$
- $\kappa = 0.7$  (females) or  $0.9$  (males)
- $\alpha = -0.248$  (females) or  $-0.207$  (males)

The eGRF will further be calculated by sMDRD (Levey et al., 2007):

- $$\text{eGFR [mL/min/1.73 m}^2\text{]} = 175 \times (\text{serum creatinine [mg/dL]})^{-1.154} \times (\text{age [years]})^{-0.203} \times 0.742 \text{ [if female]} \times 1.212 \text{ [if black]}$$

The following dose equivalents for Furosemid i.v. will be used:

- 20 mg Furosemid i.v. = 40 mg Furosemid p.o.
- 20 mg Furosemid i.v. = 20 mg Torasemid p.o.

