### 4.2 Secondary endpoints

- To evaluate how estimated PV (ePV) and estimated total blood volume (TBV) assessments on days 1 and 3 (by established measures such as Nadler's formula or Metropolitan Life Tables) predict measured PV (mPV; as assessed by FAST methodology) and measured TBV (mTBV; calculated from mPV and measured hematocrit) at these time points.
- To evaluate how a clinical evaluation (including a reasonable subset of the variables age, gender, BMI, hematocrit, edema grade, presence of pulmonary rales, presence of jugular venous congestion, arterial blood pressure, NYHA stage, respiratory rate) on days 1 and 3 predicts mPV and mTBV at these time points.
- To evaluate whether eGFR calculation by the CKD-EPI formula on days 1 and 3 provides an accurate estimate of measured GFR (mGFR; by assessed by FAST methodology) in heart failure patients undergoing active fluid management.
- To evaluate whether patients with a low mGFR/eGFR ratio on days 1 and 3 are at higher risk of developing AKI within the following 48-72 hours.
- To evaluate whether ranges of mPV (low mPV, normal mPV, high mPV) and/or mTBV (low mTBV, normal mTBV, high mTBV) on days 1 and 3 are associated with subjectively reported symptoms (PGA, dyspnea, dizziness, nausea)

determined using patient symptom assessment sheets within the following 24-48 hours.

- To evaluate whether patients with low mPV or low mTBV (cutoffs potentially adjusted for some of the following variables age, gender, body height, body weight, optimal body weight (dry weight), hematocrit) on day 1 or on day 3 are at risk of developing low-output complications within the next 24-48 hours (e. g. subjectively reported dizziness/nausea, PGA, hypotension, need for iv-fluid therapy).
- To evaluate whether patients with a high mPV or a high mTBV (cutoffs potentially adjusted for some of the following variables age, gender, body height, body weight, optimal body weight (dry weight), hematocrit) on day 1 and/or day 3 are at risk of being refractory to diuretic therapy (e. g. require dosage increases of furosemide/torsemide, require ultrafiltration/RRT within the next 24-48 hours, fail to improve subjectively in PGA and dyspnea scales).
- To evaluate whether the time course of ePV and estimated TBV (eTBV) from day 1 to day 3 adequately reflects the time course of mPV and mTBV at these time points.

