To evaluate whether eGFR calculation by the CKD-EPI formula and sMDRD formula on days 1 and 3 provides an accurate estimate of measured GFR (mGFR; assessed by FAST methodology) in heart failure patients undergoing active fluid management, linear regression models with the measured value at a given day as dependent variable and the estimated version as independent variable will be generated. The models will be adjusted for mPV and mPVS. Further, Bland-Altman plots will be generated comparing the estimated and measured parameters separately for day 1 and day 3. The defined limits of agreements are  $\pm 6\text{ml/min}$ . Diagnostic accuracy including frequencies of values between 15% and 30% of the measured value will be determined as mentioned before.

To evaluate whether patients with a low mGFR/eGFR ratio on days 1 and 3 are at higher risk of developing AKI within the following 72 (day 1) and 48 (day 3) hours, logistic regression models with the AKI status as dependent variable and mGFR/eGFR ratio as independent variables will be generated. The models will be adjusted for mPVS, mTBVS. Three different versions of the mGFR/eGRF ratio will be evaluated: ratio  $< 1$ ; ratio  $<$  first quartile; ratio as continuous parameter.

To evaluate whether ranges of mPVS (low mPVS ( $< -10\%$ ), normal mPVS ( $-10$  to  $+10\%$ ), high mPVS ( $> +10\%$ )) and/or mTBVS (low mTBVS ( $< -10\%$ ), normal mTBVS ( $-10$  to  $+10\%$ ), high mTBVS ( $> +10\%$ )) on days 1 and 3 are associated with subjectively reported symptoms (current PGA  $> 15$ , current dyspnea  $> 15$ , current dizziness  $> 15$ , current nausea  $> 15$ ) determined using patient symptom assessment sheets within the following 24-48 hours, a logistic regression

---

model with occurrence of symptoms (PGA, dyspnea, dizziness, nausea) as dependent variable and the categorized measured value (mPVS, mTBVS) as independent variables will be generated. The models will be adjusted for mean arterial pressure.

To evaluate whether patients with low mPVS ( $< -10\%$ ) or low mTBVS ( $< -10\%$ ) on day 1 or on day 3 are at risk of developing low-output complications within the next 24-48 hours (subjectively reported dizziness  $> 15$ , nausea  $> 15$ , PGA  $< 25$ , hypotension (Systolic  $< 100$ , diastolic  $< 60$  mmHg), need for iv-fluid therapy), logistic regression models using mPVS and mTBVS as independent variables will be used.

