## 8 Changes from the protocol

In general, no variable selection will be done in the regression models due to limited sample size. Rather clinical expertise regarding the most important explanatory variables will be used to determine a fixed, hierarchical set of possible covariates.

The mPVS and mTBVS are used to determine patients with low, normal or high PV and TBV and thus, the status will be defined based on established estimation formulas for ideal PV and TBV incorporating weight and/or height.

The analysis of the time course of estimated and measured PV and TBV via t-tests was replaced by Bland-Altman-analyses since these analysis better reflects the underlying question of clinically equivalent measurements. Further, the curve characteristics (e.g. times when maximal and minimal volumes are reached and the areas under the curve) based on only few time points were deemed to be of minor meaningfulness.

Haemoglobin for estimating plasma volume changes by Strauss formula and cystatin C values to estimate Glomerular Filtration Rate were also recorded during the study and will also be utilized for the analysis in the respective estimation formulas.

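### The ideal total blood volume in SAP 7.2 has no sex term, while the SAP's own Nadler estimate does; the two references differ by sex by nearly the ±10% class limit, and no model using mTBVS contains gender

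*SAP*

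**What the plan says.** SAP 7.2 gives the "Nadler formula for eTBV" with different constants for men and women. Kaplan-Hakim ePV and the ideal plasma volume are also split by sex; for the latter the women's line is "Women: iPV [mL] = 40 [mL/kg] × weight [kg"], against 39 mL/kg in men. The "Lemmens-Bernstein-Brodsky formula for ideal TBV (iTBV") has one equation for both sexes, in BMI and weight, using the lowest weight of days 1 to 5. eTBVS and mTBVS are the percentage deviations of estimated and measured volume from that iTBV.

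SAP 7.7.1 sets low below -10%, normal from -10% to +10% and high above +10%, regardless of sex. Of the symptom models it says: "The models will be adjusted for mean arterial pressure". The low-output models name only mPVS and mTBVS. The AKI models use mTBVS as an adjustment variable. The models for remaining stay, dialysis/ultrafiltration, rehospitalisation and mortality use day 1 or day 3 mPVS and mTBVS, or their changes. None of these names gender. SAP 7.8 plans no subgroup analyses.

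Protocol 4.2 had the "cutoffs potentially adjusted for some of the following variables age, gender, body height, body weight" and further items. SAP 8 replaces this: "the status will be defined based on established estimation formulas for ideal PV and TBV incorporating weight and/or height". It does not mention that sex is thereby left out of the TBV reference.

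**The concern.** A status score should mean the same thing in every patient. If the reference volume ignores sex while expected volume at a given height and weight differs by sex, a fixed ±10% limit asks different things of men and women. The low class then collects women and the high class collects men, partly for reasons unrelated to fluid status.

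Such a score would be confounded with sex. Any outcome that differs by sex for other reasons could then appear as an effect of blood volume, with no term in the models to absorb it. The trial's stated aim is to generate hypotheses for phase III, so a sex difference read as a volume signal would be a misleading product even in a descriptive analysis.

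**Working it through.** The documents give no figure for this point, so there is none to reproduce. The formulas come from SAP 7.2. Body sizes and volume distributions are assumptions, because the documents give none. Protocol 3.1.3.3 labels the Nadler coefficients as plasma volume; I follow the SAP's label, total blood volume.

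**Step 1: one body.** Since BMI = w/h², iTBV = 70 × sqrt(22) × h × sqrt(w) = 328.3 × h × sqrt(w) mL. At 1.70 m and 70 kg:

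- iTBV = 328.3 × 1.70 × 8.367 = 4670 mL, both sexes.
- Nadler, man: 0.3669 × 4.913 + 0.03219 × 70 + 0.6041 = 4.660 L, so status = 4660/4670 - 1 = -0.2%.
- Nadler, woman: 0.3561 × 4.913 + 0.03308 × 70 + 0.1833 = 4.248 L, so status = 4248/4670 - 1 = -9.0%.
- Gap: 8.8 points.

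**Step 2: other bodies, identical in both sexes.**

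| Height, weight (BMI) | Man | Woman | Gap (points) |
|---|---|---|---|
| 1.55 m, 55 kg (22.9) | -0.9% | -11.8% | 10.9 |
| 1.65 m, 70 kg (25.7) | -0.6% | -9.6% | 9.0 |
| 1.70 m, 80 kg (27.7) | -0.2% | -8.3% | 8.1 |
| 1.80 m, 120 kg (37.0) | +2.0% | -3.8% | 5.8 |

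Over heights 1.55-1.80 m and BMI 20-40 in fine steps, the gap runs from 5.5 to 11.9 points, mean 8.1.

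**Step 3: equal BMI, typical heights (man 1.76 m, woman 1.62 m).** The gap is 10.5 points at BMI 25, 9.7 at 28, 9.3 at 30 and 8.4 at 35. If weight falls by 3 kg between the measurement and the lowest weight, the gap changes by about 0.1 point.

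**Step 4: classes if true volume follows Nadler.** Assume true volume centred 5% above Nadler, SD 12%, BMI 29, heights as in step 3. Nadler/iTBV is 1.0035 in the man and 0.908 in the woman.

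- Man: centre 1.05 × 1.0035 - 1 = +5.4%, SD 12 × 1.0035 = 12.0. Low: Φ((-10 - 5.4)/12.0) = 10%. High: 1 - Φ((10 - 5.4)/12.0) = 35%.
- Woman: centre 1.05 × 0.908 - 1 = -4.6%, SD 12 × 0.908 = 10.9. Low: Φ((-10 + 4.6)/10.9) = 31%. High: 1 - Φ((10 + 4.6)/10.9) = 9%.

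Simulation with BMI (SD 5) and height varying gives nearly the same: about 30% against 10% low, and 10% against 36% high. With the centre from 0 to +10% and SD from 8% to 20%, low covers about 9-48% of women and 0.5-30% of men; women exceed men in every combination.

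**Step 5: classes if the sex-free formula is right.** Centre true volume 5% above iTBV in both sexes, SD 12%. Low is Φ(-15/12) = 11% and high is 1 - Φ(5/12) = 34%, for men and women alike. There is no artefact.

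**Step 6: within-patient change.** iTBV is the same on day 1 and day 3, so the offset cancels and only the scale differs. A 400 mL fall in the woman of step 1 is 400/4670 = 8.6% against iTBV and 400/4248 = 9.4% against Nadler.

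**The case against.** The strongest objection is that mTBVS compares a measured volume with iTBV, and Nadler does not enter it. A sex artefact in mTBVS exists only if women's true volume follows Nadler. That stands. A reader might infer that low mTBVS is partly a label for being female and that women with high volume are missed. The documents do not support this as fact: they hold two references that disagree and do not show which is right.

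A reader might also infer a large excess of false positives. With 50 patients (20 women), no volume effect and a sex difference in stay of 0.5-0.8 SD, mTBVS as sole regressor reached p<0.05 in 6-28% of simulated trials. But that sex difference is not in the documents, and the SAP's outcome models enter mPVS and mTBVS together. In that joint model, with volume SD 12%, the rates are about 8% and 12%; for a sex difference of 0.2-0.3 SD they are 5-7%. So no particular error rate is claimed.

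Nor is this a broken commitment. The protocol said only that cut-offs might be adjusted for some of a list, and SAP 8 discloses the change. SAP 8 also speaks of a fixed set of possible covariates, but 7.7.1 names gender only in the models that predict mPV and mTBV.

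Finally, all p values are descriptive, and the comparison of improving with worsening mGFR already includes gender among its baseline characteristics. Both points are correct and limit the weight of the matter. They do not make the class tables or the regressions interpretable by sex.

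**Conclusion.** The inconsistency is certain: SAP 7.2 contains two total-blood-volume references whose disagreement depends on sex, by about 5-12 points at identical body size (mean about 8) and about 8-10 points at typical heights with equal BMI. That is close to the whole distance from zero to the class limit. The misclassification in step 4 is conditional on women's true volume following Nadler, and its size depends on the assumed centre, SD and body sizes.

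Affected are the analyses that use the level or class of mTBVS: symptoms, low-output complications, AKI adjustment, the day 1 and day 3 outcome models, and the mGFR comparisons that start from high or low TBVS. eTBVS is affected in the comparison of improving with worsening mGFR. The diuretic-refractory model is affected only if its regressor is mTBVS: the SAP defines high by mTBVS but then names mPV and mTBV as regressors.

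Not affected are the primary endpoint, PVS (whose reference is sex-specific) and the Bland-Altman comparisons. Within-patient changes are largely unaffected. This is worth correcting before analysis, but it does not threaten the trial's main result.

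**What to change.** 1. Report the low, normal and high mTBVS classes by sex, for day 1 and day 3.
2. Add gender as a covariate to the models that use mTBVS level or class, where the SAP's rule of at least 10 observations per parameter allows. That rule is written for the models predicting mPV and mTBV, so the SAP should say how it applies to binary outcomes and mortality, where events are the scarce quantity. Where gender cannot be carried, say so and point to the table by sex.
3. As a sensitivity analysis for mTBVS only, recompute it against the SAP's Nadler equations for men and women at the lowest day 1-5 weight. A patient whose volume equals that value then scores 0% in either sex.
4. Do not use Nadler as the reference for eTBVS. eTBV is itself the Nadler value, so the score would show only weight change: for a 3 kg loss, 0.097/5.299 L = +1.8% in a man of 1.76 m and 86.7 kg, and 0.099/4.029 L = +2.5% in a woman of 1.62 m and 73.5 kg.
5. State in SAP 8 that the TBV reference does not use sex.

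The cost is SAP wording, a few extra tables and one more parameter in small models. Height, weight, haematocrit and gender are already collected. The main iTBV formula can stay as it is.

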#### 4.3.2 Safety/Tolerability

- Length of stay, dialysis/ultrafiltration requirement, or rehospitalization within 30 days, or mortality
- Laboratory values (Serum creatinine (mg/dl), Hematocrit (%), creatine phosphokinase (CPK) (U/l), NT-proBNP (ng/l), Alanine aminotransferase (ALT) (U/l), Aspartate aminotransferase (AST) (U/l), Alkaline phosphatase (AP) (U/l), bilirubin, total and direct (mg/dl), INR (dimensionless)) collected on day 1, 3, 5 (except for serum creatinine which is collected on all days and hematocrit which is only collected on day 1)
- Occurrence of AEs and SAEs
- Routine clinical parameters (Serum creatinine on admission (mg/dl), Baseline serum creatinine (nadir from inspection of previous, lab values or by primary care physician) (mg/dl), Serum creatinine (mg/dl), Serum sodium (mmol/l), Serum potassium (mmol/l), eGFR (CKD-EPI) (ml/min/1.73 m^2), Hemoglobin (g/dl), Serum-Albumin (g/dl), Urine output (0:00 - 24:00 on the indicated day) (ml/24 h) (if, incomplete, extrapolate the available time period to 24 hours), Chest X-ray: evidence of pulmonary congestion, Chest X-ray: evidence of pleural effusion, Chest X-ray: evidence of cardiomegaly, Alanine aminotransferase (ALT) (U/l), Aspartate aminotransferase (AST) (U/l), Alkaline phosphatase (AP) (U/l), Bilirubin, total and direct (mg/dl))

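### SAP 7.2 omits the division by 100 on hematocrit in the Kaplan-Hakim and Strauss formulas; coded literally, estimated plasma volume is negative and the Strauss change does not track plasma volume

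*SAP*

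**What the plan says.** SAP 7.2 lists the derived volumes. For mTBV, measured plasma volume is divided by a plasma fraction in which hematocrit is scaled: "1 - \text{hematocrit [\%]} / 100".

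Under "Kaplan-Hakim Formula for ePV" the scaling is gone. Men have "1 - \text{hematocrit [\%]}) \times [1530 + (41 \times \text{weight [kg" and women have "1 - \text{hematocrit [\%]}) \times [864 + (47.9 \times \text{weight [kg". The "Strauss formula for plasma volume change" multiplies a hemoglobin ratio by a ratio of plasma fractions, again unscaled: "1 - \text{hematocrit\_2 [\%]}) / (1 - \text{hematocrit\_1 [\%]}) \times 100". The section adds that plasma volume change will also be taken as the ratio of Kaplan-Hakim values.

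Hematocrit is held in percent. SAP 4.3.2 lists "Hematocrit (%), creatine phosphokinase (CPK) (U/l" among the laboratory values, and protocol Table 7 gives the same unit. Nothing in the SAP says that hematocrit is turned into a fraction before use.

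These quantities are used in SAP 7.7.1. ePV enters the regressions, Bland-Altman plots and accuracy measures against mPV. The change in ePV and the Strauss change are compared with the change in mPV from day 1 to day 3. ePVS, built on ePV, is compared between patients with improving and worsening mGFR.

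**The concern.** The same variable, with the same unit label, is scaled in one formula and not in the others a few lines later. They cannot all be right under one convention.

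At stake is the comparison of estimating formulas with the FAST measurement. The protocol synopsis hypothesizes that quantitative measurements will differ from estimating equations. A unit error that makes the estimates fail would produce disagreement in the hypothesized direction. The outlier inspection in SAP 5.2 names hematocrit, weight, eGFR and the FAST measurements, but neither ePV nor the Strauss change. The planned data review is therefore not directed at the derived values where the error would show.

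**Working it through.** The documents give no worked value for ePV or plasma volume change, so there is no figure of the plan's own to reproduce. The formulas are those of SAP 7.2. The patient values are assumptions chosen for illustration. H is hematocrit in percent and Hb is hemoglobin in g/dL.

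**1. ePV.** Man, 80 kg, H = 40.
- As printed: (1 - 40) × (1530 + 41 × 80) = -39 × 4810 = -187,590 mL.
- With H/100: 0.60 × 4810 = 2,886 mL.

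Woman, same values: -39 × (864 + 47.9 × 80) = -39 × 4696 = -183,144 mL, against 0.60 × 4696 = 2,818 mL.

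Because 1 - H is negative for any H above 1, every realistic patient has a negative ePV. For the man, with ideal PV 39 × 80 = 3120 mL, ePVS is (-187,590 - 3120)/3120, about -6112%, against (2886 - 3120)/3120 = -7.5%.

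**2. Ratio of Kaplan-Hakim values.** H rises from 36 to 40 at equal weight, so the weight term cancels.
- As printed: (1 - 40)/(1 - 36) = 39/35 = 111.4%.
- With H/100: 0.60/0.64 = 93.8%.

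The minus signs cancel, so hemoconcentration reads as a gain in plasma volume.

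**3. Strauss change.** Hb 12 to 13, H 36 to 39.
- As printed: 12/13 × 38/35 = 100.2%.
- With H/100: 12/13 × 0.61/0.64 = 88.0%.

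The reason is algebraic. (1 - H2)/(1 - H1) equals (H2 - 1)/(H1 - 1), which is close to H2/H1. If Hb and H move in proportion, Hb1/Hb2 equals H1/H2 and the two factors nearly cancel. Further cases with Hb = H/3:

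| H day 1 to day 3 | As printed | With H/100 |
|---|---|---|
| 36 to 40 | 100.3% | 84.4% |
| 40 to 36 | 99.7% | 118.5% |
| 30 to 36 | 100.6% | 76.2% |
| 36 to 30 | 99.4% | 131.3% |

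**4. When Hb and H do not move in proportion.** Take H 36 to 40 and let the Hb/H ratio shift between days.

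| Shift in Hb/H | As printed | With H/100 |
|---|---|---|
| -2% / +2% | 102.3% / 98.3% | 86.1% / 82.7% |
| -5% / +5% | 105.6% / 95.5% | 88.8% / 80.4% |
| -10% / +10% | 111.4% / 91.2% | 93.8% / 76.7% |

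The printed result follows the mismatch, while the plasma volume loss that the corrected formula shows throughout is lost.

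**5. Simulation.** Assumptions: hematocrit mean 38 and SD 5, constant red-cell volume, true plasma volume change with SD 7%, and independent error on each Hb and hematocrit reading.

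| Error per reading | Printed: SD (points) | Printed: 95% range | Printed: correlation with true change | Corrected: correlation |
|---|---|---|---|---|
| 1% | 2.0 | about 96 to 104 | -0.06 | 0.97 |
| 2% | 4.1 | about 92 to 108 | -0.03 | 0.90 |

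With no reading error at all, the printed SD is only 0.12 points.

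**The case against.** **The label may mean a fraction.** SAP 7.2 is loose with its percent sign. The four volume-status formulas are labelled in percent but carry no factor of 100, although SAP 7.7.1 applies cut-offs of -10% and +10% to the measured statuses. If 40% is read as 0.40, the Kaplan-Hakim and Strauss formulas are correct. This has some force: the defect is one of unit notation, and every consequence above depends on literal coding with 40 entered as 40. It does not remove the need for a correction, because on that reading mTBV is wrong instead. With mPV 3000 mL and hematocrit 0.40 it would give 3000/(1 - 0.40/100) = 3,012 mL, against 3000/0.60 = 5,000 mL. The recording unit and the explicit division in mTBV favour percent.

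**A programmer would catch it.** For ePV, very likely. Both formulas take the same hematocrit variable, so rescaling that variable would repair Strauss too. A reader might infer that the Strauss error is bound to pass unnoticed; the documents do not support that. The risk is narrower: a repair confined to the ePV line leaves Strauss wrong, and a repair of the variable upsets mTBV as printed.

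**The Strauss value would not be 100% for everyone.** This is right. A reader might infer that every patient would show no change, but that needs hemoglobin and hematocrit to move in proportion and be measured without error. Protocol Tables 7 and 8 list hematocrit as a study measurement and hemoglobin as a routine one, so they need not come from the same sample. The result would then scatter around 100%. The loss of tracking remains.

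**The analyses are secondary.** Also right. SAP 7.1 calls all analyses descriptive, and the primary analysis in SAP 7.6 uses none of these formulas. Strauss is one of several change measures.

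**Conclusion.** The inconsistency is real and needs correcting whichever way the percent label is read. Under the recording unit, the Kaplan-Hakim formulas for both sexes and both hematocrit terms of Strauss are wrong as printed. Coded literally, they give an absurd ePV, a reversed ePV ratio, and a Strauss change whose correlation with true change is near zero under 1 to 2% reading error.

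The direction of the ePV and ratio errors follows from the algebra at any realistic hematocrit when weight is equal on the two days. The spread and correlations for Strauss rest on the assumed hematocrit distribution, the 7% SD of true change and the assumed reading errors, none of which the documents give.

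The documents contain neither code nor results, so they do not show that any analysis has been done wrongly. The point concerns the specification of secondary, descriptive analyses and has no bearing on the primary safety or FD003 stability conclusions.

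**What to change.** In SAP 7.2, write (1 - hematocrit [%] / 100) in the Kaplan-Hakim formulas for men and women, and in the numerator and denominator of the Strauss formula, so that they match mTBV. Confirm that any program already written does the same and that it does not also rescale hematocrit on input, which would apply the division twice. One worked example per formula, such as 2,886 mL and 88.0% from the cases above, would help program checking but is optional.

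The cost is a change of SAP wording and a code check. No data, design or conduct is affected.

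### Ideal plasma volume is linear in weight while ideal blood volume is BMI-corrected, so the mPVS categories partly encode BMI

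*SAP*

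**What the plan says.** SAP 7.2 gives two reference volumes.

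- **Ideal PV (iPV):** the "Harrison formula for ideal PV", 39 mL/kg for men and 40 mL/kg for women, with no height or BMI term.
- **Ideal TBV (iTBV):** the Lemmens-Bernstein-Brodsky formula, 70 mL/kg divided by sqrt(BMI/22). Here "the lowest body weight during the days 1 to 5 will be used for calculation of BMI". The same lowest weight multiplies both per-kg figures.

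Plasma volume status is then "mPVS [%] = Percentage change from iPV: (mPV - iPV)/iPV". mTBVS is built the same way from mTBV and iTBV, with mTBV = mPV/(1 − hematocrit).

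In SAP 7.7.1 the symptom objective, which begins "To evaluate whether ranges of mPVS (low mPVS", sets low as below −10%, normal as −10% to +10% and high as above +10%, for mPVS and mTBVS alike. The symptom models adjust for mean arterial pressure only. The low-output models list no covariate beyond the two statuses.

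SAP section 8 gives the reason for using statuses: "the status will be defined based on established estimation formulas for ideal PV and TBV incorporating weight and/or height". It does not mention that BMI enters one ideal and not the other.

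**The concern.** The two statuses come from one measured quantity, mPV, and share one set of cut-offs. A reader will take them as two views of the same thing. If their references scale differently with body size, heavier patients drift towards low PV and leaner ones towards high PV, with no difference in mTBVS.

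Two readings are then at risk. An association of PV status with symptoms or low-output complications may be partly an association with body size. And disagreement between the PV and TBV results may be taken for physiology when the formulas produced it. SAP 7.1 says the aim is to generate hypotheses for phase III, so a wrong lead has a cost even though all analyses are descriptive.

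**Working it through.** The plan states no figure on this point, so there is none to reproduce. The formulas and cut-offs are from SAP 7.2 and 7.7.1. Patient BMI and hematocrit (Hct) are **assumptions**: the documents list both variables but give no distribution, and eligibility sets no BMI limit. Results are therefore shown over a range.

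**1. Ratio of the two statuses.** Let W be the lowest weight and k = 39 (men) or 40 (women).

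- 1 + mPVS = mPV / (k × W)
- 1 + mTBVS = [mPV/(1 − Hct)] / [W × 70/sqrt(BMI/22)]
- Dividing: (1 + mPVS)/(1 + mTBVS) = 70(1 − Hct) / [k × sqrt(BMI/22)]

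mPV and W cancel. What separates the statuses is hematocrit, sex and BMI.

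**2. Man, Hct 40%, mTBVS exactly 0%.** mPVS = iTBV per kg × 0.60/39 − 1.

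| BMI | iTBV, mL/kg | mPVS | Class |
|---|---|---|---|
| 22 | 70.0 | +7.7% | normal |
| 30 | 59.9 | −7.8% | normal |
| 35 | 55.5 | −14.6% | low |
| 40 | 51.9 | −20.1% | low |

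In volumes: a man of 1.75 m and 107.2 kg (BMI 35) has iTBV 5949 mL. At that blood volume his PV is 5949 × 0.60 = 3569 mL. His iPV is 39 × 107.2 = 4180 mL, so mPVS = −14.6%.

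**3. Threshold BMI at mTBVS 0%.** Low PV applies above 22 × [70(1 − Hct)/(0.9k)]². High PV applies below 22 × [70(1 − Hct)/(1.1k)]². For a man at Hct 40%, the low threshold is 22 × (42/35.1)² = 31.5.

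| Hct | Men: low above | Men: high below | Women: low above | Women: high below |
|---|---|---|---|---|
| 30% | 42.9 | 28.7 | 40.8 | 27.3 |
| 35% | 37.0 | 24.7 | 35.1 | 23.5 |
| 40% | 31.5 | 21.1 | 29.9 | 20.0 |
| 45% | 26.5 | 17.7 | 25.2 | 16.8 |

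**4. Opposite labels.** A man with Hct 40%, BMI 40 and mTBVS +11% has mPVS = 1.11 × 0.7987 − 1 = −11.3%. He is high TBV and low PV from one measurement.

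**5. Where the ideals agree.** They coincide at Hct = 1 − k × sqrt(BMI/22)/70. For men this is 44.3% at BMI 22, 34.9% at BMI 30, 29.7% at BMI 35 and 24.9% at BMI 40.

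**6. Where mPVS enters SAP 7.7.1.**

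- Symptom models: categorised status.
- Low-output models: mPVS and mTBVS.
- Models for length of stay, dialysis/ultrafiltration, rehospitalization and mortality: the second to fourth use the statuses or their changes; the first uses absolute volumes.
- Comparisons of mGFR change between groups with high, or low, PVS or TBVS on day 1. The man in step 4 qualifies for both the high and the low starting group.

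The direction of a patient's change in mPVS from day 1 to day 3 is not affected, because iPV is the same on both days.

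**The case against.** **Which ideal is wrong?** A reader might infer that the linear iPV is in error. The algebra shows only that the two references conflict. If the linear iPV were right, mTBVS would be the biased index. SAP 7.2 attributes iPV to a published source, which the SAP's reference list shows to be a study of plasma volume status in chronic heart failure. This objection stands.

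**Does low PV largely mean obese?** The documents do not support that. The label depends on hematocrit: a man with BMI 30 and Hct 40% is normal at −7.8%, and at Hct 30% a man with ideal TBV is not low until BMI 42.9. The calculation also fixes mTBVS at 0%, whereas decompensated patients will vary in true volume. PV and TBV status may differ legitimately through red-cell mass. Confounding would further require BMI to affect the outcomes, which is not shown.

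**Is diuretic refractoriness affected?** A reader might count it in. SAP 7.7.1 poses that question for high mPVS or mTBVS but states the models with absolute mPV and mTBV, which use neither ideal.

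**Would rescaling iPV settle it?** Taking iPV as iTBV × 39/70 (men) or × 40/70 (women) removes BMI from the ratio, but it assumes iTBV is right and fixes a reference hematocrit of 1 − 39/70 = 44.3% or 1 − 40/70 = 42.9%. At mTBVS 0%, every man with Hct below 1 − 1.1 × 39/70 = 38.7% would then be high PV at any BMI. That is a good reason not to replace the published index.

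**Is it already handled?** Status is defined openly, mTBVS runs alongside, BMI is a baseline variable and everything is descriptive. That limits the harm. It does not let a reader separate a PV-status association from a body-size one, because the symptom and low-output models carry no body-size term.

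**Conclusion.** The mismatch is exact and follows from the SAP's own formulas. At fixed mTBVS and hematocrit, 1 + mPVS is proportional to 1/sqrt(BMI), so the mPVS categories partly encode BMI. From BMI 22 to 40, a man with ideal TBV and Hct 40% moves from +7.7% to −20.1%, a shift wider than the 20-point normal band. The BMI at which he becomes low runs from 26.5 to 42.9 as hematocrit goes from 45% to 30%.

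The thresholds rest on mTBVS of 0% and on assumed hematocrits. The number of patients whose categories disagree cannot be derived from the documents, nor can the correct reference. The reach is limited to the descriptive secondary analyses listed above. Related AEs and FD003 stability, the primary endpoints, do not use either ideal. This is a cheap improvement to interpretability, not a flaw that undermines the trial's main conclusions.

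**What to change.** Keep the published iPV as the main index and add the following to SAP 7.7.1.

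- **Sensitivity run.** Repeat the symptom and low-output models with BMI as covariate, calculated from the same lowest weight as in 7.2. Fit mPVS and mTBVS in separate models: once BMI is in, the two differ only through hematocrit and sex, so a joint model would say little about volume.
- **Tables.** Cross-tabulate mPVS against mTBVS categories for day 1 and day 3, and report BMI and hematocrit by category.
- **Interpretation rule.** Do not read disagreement between PV and TBV results as physiology without these tables.
- **Optional.** A BMI-scaled iPV may be shown as an exploratory index only, noting that it assumes the iTBV formula and a reference hematocrit of about 44% (men) or 43% (women).

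The cost is a few tables and one extra parameter in small logistic models. SAP 7.7.1 asks for 10 observations per estimated parameter in its clinical-evaluation models. By that yardstick, a symptom model with intercept, two category terms, mean arterial pressure and BMI has 5 parameters and needs 5 × 10 = 50 observations, the whole planned sample. Event counts may be tighter still. Where the BMI run is not supportable, the tables alone should be reported.
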